**Specific Aim 1:** Our first goal is to compare postural control in subjects assigned to use the active Electrical Stimulation (intervention group) and subjects assigned to non-functional stimulator (sham group). Balance will be assessed for both groups at baseline and at bi-weekly intervals. Static balance and postural compensatory strategy will be assessed using the body worn sensor technology (BalanSens™) explained in the preliminary study #1. The duration of assessment is approximately five minutes. The test includes quiet upright standing for a period of at least 30 seconds under two conditions: eyes-open and eyes-closed. Postural control will be quantified by measuring the range of motion of center of mass (COM) in medial-lateral and anterior-posterior direction. COM is estimated using an innovative and validated technology based on wearable sensors as explained in our preliminary study #1 – Figure 12. The key advantage of this technology is that balance is assessed outside of gait laboratory and directly in our podiatric center. Additionally, it allows measuring directly COM instead of center of pressure (COP). Our recent study suggests that measuring COM is 12 times more sensitive to assess postural instability than COP (Figure 3) (Najafi, Horn et al. 2010).

**Figure 12:** Balance will be assessed according Romberg protocol and will be quantified using a validated technology based on body worn sensors

**Figure 13:** An innovative device based on body worn sensors allows measuring spatio-temporal parameters of gait and gait initiation in free condition including outside of a gaitlab.

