To determine whether gait, balance, and physical activity variables change significantly across different study visit epochs, within-subject analyses of variance (ANOVA's) will be employed. We assume that plantar electrical stimulation is helpful to improve subjects gait, balance, and physical activity. Then sensor-derived movement variables should change substantially from baseline to the end of the study for the active group with no significant change in placebo group. For example, the range of motion of COM and RCI values should be reduced and gait velocity should be increased. Next, for all continuous variables, pretreatment scores will be regressed on post-treatment scores to form residualized change scores (e.g. VPT, monofilament test, pain intensity, A1C, etc). Correlations will then be generated among these scores to determine whether changes in sensor-derived movement factors are related appropriately with increases in (clinically assessed) functional capacities and self-report measures of activities, mood, socializing, etc. ANOVA test will be used to examine significant difference between intervention and sham group at baseline for age and BMI as well as the indicated outcomes (e.g. gait, balance, VPT, ABI,. Etc). We assumed there is no significant difference between sham and intervention group at baseline for the indicated variables. The same test will be repeated for the week 12. We assumed that the outcomes of study will be improved in the intervention group compared to the sham group. Paired- sample t-test will be used to examine the retention of the electrical stimulation therapy at two weeks post stopping the therapy compared to week-12. We assumed the benefit of the electrical stimulation therapy will be retained at least for two weeks. Additional analyses will examine the degree to which early-treatment changes in cognitive variables and functional capacity variables (representing functional restoration processes) predict late-treatment changes in moving ability post plantar electrical stimulation therapy. Such analyses will also allows to elucidate the relative contributions fear of falling (assessed using FES score); and/or and range of motion (assessed using body worn sensors) made to bringing about clinically meaningful changes in gait balance control. Moderator effects will also be examined for exploratory purposes. Using gender as an example, mixed design ANOVA's will be conducted to determine whether gait and balance factors change over the course of treatment at different rates or with different patterns for men and women as well as for patients with high or low severity of neuropathy and peripheral vascular disease. We assume those who have higher peripheral vascular problem will receive maximum benefit from electrical stimulation. Additional analyses will test whether changes in gait and balance variables predict changes in clinically important outcome factors (e.g., fear of falling (FES) , quality of life (SF12), adverse events, foot ulcer, etc) depending on gender.

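### The analyses linking gait and balance changes to clinical changes do not say how treatment arm is handled; if the arms are pooled, a shared treatment effect can pass for an association

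*Combined protocol and SAP*

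**What the plan says.** Section 14, Analysis Plan, describes three related steps in addition to the group comparisons.

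- **Correlation.** Residualized change scores are formed for the continuous variables. Then: "Correlations will then be generated among these scores to determine whether changes in sensor-derived movement factors are related appropriately with increases in" clinically assessed function and self-reported measures.
- **Contributions.** Early changes in cognitive and functional variables are examined for how far they "predict late-treatment changes in moving ability post plantar electrical stimulation therapy". The same analyses are to weigh the contribution of fear of falling (FES score) against that of "range of motion (assessed using body worn sensors) made to bringing about clinically meaningful changes in gait balance control".
- **Prediction.** "Additional analyses will test whether changes in gait and balance variables predict changes in clinically important outcome factors". The examples given are "fear of falling (FES) , quality of life (SF12), adverse events, foot ulcer, etc) depending on gender".

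None of these sentences names an arm term, an analysis set or a model. The same section does name the intervention and sham groups where it compares them at baseline and week 12.

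On expected effects, the section says the sensor-derived movement variables "should change substantially from baseline to the end of the study for the active group with no significant change in placebo group". Specific Aim 3 (Hypotheses 4 and 6) expects better quality of life in the intervention group and less fear of falling than under sham. Specific Aim 1 defines the balance measure: "Postural control will be quantified by measuring the range of motion of center of mass (COM) in medial-lateral and anterior-posterior direction".

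**The concern.** The plan's own hypotheses make arm a common cause of both sides of these associations. If stimulation reduces sway and also lowers FES scores, active patients sit at one end of both scales and sham patients at the other. A correlation across all patients then appears even if, within each arm, the patients whose sway improved most are no more likely to report less fear. Residualizing on baseline does not remove this, because randomization leaves the arm effect in the residual.

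What is at stake is interpretation. A significant result could be reported as sensor changes tracking clinical benefit when it only restates the treatment effect. FES is a contributor to balance change in one sentence and an outcome of balance change in another, so an arm-driven association would seem to support either direction. Section 14 applies a two-sided 0.05 threshold unless otherwise noted and labels only the moderator analyses exploratory.

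A separate issue arises in the contributions sentence. Sensor range of motion is a predictor of balance change there, while Specific Aim 1 measures balance by sensor range of motion of the center of mass (COM).

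**Working it through.** **Sample size inputs (Section 14).** 50% v 10% improvement, 85% power, two-sided 5%, 27 per group required, 40 per group enrolled, 10% dropout.

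**The plan's figure.** The usual two-proportion formula gives (1.96 × √(2 × 0.3 × 0.7) + 1.036 × √(0.25 + 0.09))² / 0.4² = 21.96, so 22 per group. With continuity correction it is 27, which matches the plan. This figure is not in dispute. It shows that 27 per group at 85% power corresponds to a detectable standardized difference of (1.96 + 1.036) × √(2/27) = 0.82 SD.

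**Evaluable patients.** 40 × 0.9 = 36 per arm, 72 in all.

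**Plausible shift in balance.** From the pilot sway data in Section 14, the difference in change is (5.41 − 3.49) − (5.23 − 4.94) = 1.63 cm². The SD of change is not given. With an assumed within-patient correlation of 0.5 to 0.8 it is 2.39 to 1.55 cm², so the shift is 0.68 to 1.05 SD. With zero correlation the shift is 0.49 SD. For FES and SF12 the documents give nothing, so a range has to be assumed.

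**Induced correlation.** Suppose two changes are independent within arm, allocation is 1:1, and treatment shifts them by dx and dy SD. The pooled correlation is

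r = dx·dy / √((4 + dx²)(4 + dy²)),

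which for dx = dy = d is d²/(4 + d²).

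**Rejection rate.** By Fisher z with n = 72, the standard error is 1/√69 = 0.120 and the critical r is 0.23. For d = 1.0, r = 1/5 = 0.20, and atanh(0.20)/0.120 = 1.68, so the rejection probability is P(Z > 1.96 − 1.68) = 39%. For d = 0.5, r = 0.25/4.25 = 0.059, and the two tails add to 7.8%.

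A simulation of 20,000 trials with 36 per arm checks this and adds the arm-adjusted test:

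| dx, dy (SD) | Induced r | Pooled, unadjusted | With arm in model |
|---|---|---|---|
| 0.3, 0.3 | 0.02 | 5.3% | 4.9% |
| 0.5, 0.5 | 0.06 | 7.9% | 4.8% |
| 0.83, 0.5 | 0.09 | 12.5% | 5.1% |
| 0.83, 0.83 | 0.15 | 24.2% | 5.1% |
| 1.0, 1.0 | 0.20 | 40.6% | 5.2% |
| 0.83, 0 | 0.00 | 4.9% | 5.2% |

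The small gap at 1.0 SD (39% v 41%) reflects the Fisher approximation. The last row is the important limit: if treatment moves only one variable, the pooled test keeps its level. The calculation applies to continuous outcomes such as FES and SF12, not to adverse events or foot ulcer.

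**Overlap of predictor and outcome.** Elsewhere Section 14 writes of the range of motion of COM; the contributions sentence says only range of motion from body-worn sensors. If COM range is meant, the predictor is the measure by which Specific Aim 1 defines postural control, and its comparison with FES as a contributor is uninformative. An arm term does not cure this.

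**The case against.** **The plan does not say that the arms are pooled.** This is correct. The text is silent, and the phrase about ability after stimulation therapy could mean treated patients only, in which case arm cannot confound. Analysing each variable on all available data does not settle it. What stands is that arm is unspecified and that the text, followed literally, gives an unadjusted analysis with gender as the only named factor.

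**The inflation depends on assumed effects on both sides.** This is also correct. The induced correlations are modest, and at 0.3 SD there is almost no inflation. The plan itself predicts effects on both sides, however, so the problem arises when its hypotheses are true.

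**Adjusting for arm might hide a real mechanism.** It would not. If balance change truly drives fear of falling, the link also exists between patients within an arm and survives the arm term.

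**The range-of-motion reading is conjecture.** Partly so. The sensors also measure hip and ankle motion (Background, Study 1), the outcome includes gait, and the sentence follows from early changes predicting late ones, so the relation may be lagged. COM range is the likely meaning but is not stated.

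**These are secondary analyses.** They are, and that limits the consequence. It does not make the unadjusted version preferable when the adjusted one is nearly free.

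**Conclusion.** The concern holds in a limited form: the handling of arm is unspecified in analyses where the plan expects arm to affect both variables. If the arms are pooled without adjustment and treatment shifts both by 0.5 to 1.0 SD, a 5% test rejects about 8% to 39% of the time at 72 patients with no within-arm association, against about 5% with arm included. This rests on 1:1 allocation, 36 evaluable per arm and assumed shifts in FES and SF12.

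Several stronger readings are tempting and are not supported:

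- A reader might infer that treatment by itself is bound to create the association. It does so only with pooling and an effect on both variables.
- A reader might convert 50% v 10% to a latent shift of 1.28 SD and reach a 70% rejection rate. Section 14 ties those rates to subjects evaluable on vibration perception and monofilament testing, not to balance, FES or SF12.
- A reader might infer that balance is certainly regressed on itself, or that range of motion must always outrank fear of falling. The first depends on an undefined term, and the second has not been shown. The overlap also concerns the contributions sentence, not the prediction of FES and SF12.
- A reader might conclude that adverse events and foot ulcer should be dropped as outcomes. The documents give no event rates on which to base that.

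The between-group treatment comparison is unaffected.

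**What to change.** In Section 14, Analysis Plan:

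1. State the analysis set for the correlation and prediction analyses, and include arm in each model. For the correlations, the equivalent is to report the pooled within-arm partial correlation.
2. Keep the baseline adjustment that the residualized change scores are meant to provide.
3. Add arm × predictor as a sensitivity analysis, to see whether the slope is similar in the two arms.
4. Define the sensor range of motion in the contributions sentence. If it is COM range of motion, do not use it as a predictor of balance change.

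The cost is SAP wording, one degree of freedom per model for arm and one more where the interaction is fitted. No new data or visits are needed.
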